5.5.2.5. Incidence of Clinical Deterioration of gMG Over Time

Incidence of clinical deterioration of gMG during the first 34 weeks for Group 1 and 2 and Weeks 8 to 34 for Group 3a and 3b will be summarized separately. The FAS will be used for this analysis. The number and percentage will be presented. Exact (Clopper-Pearson) 90% CIs for the true proportions will be presented.

5.5.2.6. MGFA-PIS at Week 26

Analysis described in Section 5.5.1.7 will be repeated including assessments up to Week 34.

5.5.2.7. Proportion of Participants Who Received Rescue Therapy Over Time

Proportion of participants who received rescue therapy during the first 34 weeks for Groups 1 and 2 and Weeks 8 to 34 for Groups 3a and 3b will be summarized separately. The FAS will be used for this analysis. The number and percentage will be presented. Exact (Clopper-Pearson) 90% CIs for the true proportions will be presented.

5.5.2.8. OLE Period Analyses

The following efficacy data collected during the OLE Period as of the data cutoff date will be listed and summarized in descriptive statistics by dose level, which is the dose received at the specific visit during the OLE Period:

- Change from Baseline in the MG-ADL total score
- Proportion of participants with at least a 2-, 3-, 4-, 5-, 6-, 7-, or 8-point improvement in the MG-ADL total score
- Change from Baseline in the QMG total score
- Proportion of participants with at least a 3-, 4-, 5-, 6-, 7-, or 8-point improvement in the QMG total score
- MGFA-PIS status
- Change from Baseline in the Neuro-QoL Fatigue total score

For efficacy endpoints, baseline is defined as the last measurement on or prior to the first dose of the PEP.

5.6. Safety Analyses

The safety and tolerability of ALXN2050 will be assessed based on the incidence of AEs, clinical laboratory findings, electrocardiograms (ECGs), vital signs findings, and Columbia Suicide Severity Rating Scale (C-SSRS). The safety analyses to be produced during the Week 8 analysis and the Week 34 analysis will be detailed in each of the subsections below. No formal hypothesis testing is planned for safety data.

5.6.1. Safety Analyses at Analysis 1 (Week 8)

All outputs for safety outcomes of the Primary Treatment Period (first 8 weeks) will be based on the SS, unless otherwise specified. All safety analyses for participants during the ALXN2050 treatment period will be based on the ALXN2050-Treated Set. Safety data will be summarized

by the actual treatment received (Groups 1, 2, 3, 3a, and 3b, as applicable). Baseline is defined as the last available assessment prior to the first dose of study intervention.

5.6.1.1. Extent of Exposure

The cumulative and total drug exposure, dose intensity and relative dose intensity, treatment duration, treatment compliance, total time on study treatment and total patient-year of exposure during the Primary Treatment Period (first 8 weeks) will be summarized descriptively by treatment group. The SS will be used for the analysis. The same analysis will be performed, including all data up to the data cutoff date during the ALXN2050 treatment period using the ALXN2050-Treated Set.

Treatment duration will be calculated (in weeks) as the difference between the date of the last dose and the date of the first dose for the period plus 1. The duration will be summarized with descriptive statistics. In addition to a descriptive summary, the number and proportion of participants who have treatment duration for a specific period will be produced.

Planned total dose amount = assigned dose level of each tablet \times daily frequency (bid) \times duration in number of days of the period.

Received total dose amount = assigned dose level of each tablet \times number of tablets received of the period. The number of tablets received is calculated as the difference between the number of tablets dispensed and the number of tablets returned.

Dose intensity is calculated as the total amount of the drug received divided by the treatment duration.

The **relative dose intensity** is calculated as the actual drug exposure of the period divided by the protocol-planned drug exposure of the period $\times 100\%$.

Expected total number of tablets for a specific period = 6 tablets/day \times duration in the number of days of the period.

Actual total number of tablets received for a specific period = total number of tablets dispensed - total number of tablets returned of the period (based on electronic case report form [eCRF] collection).

Treatment compliance is defined as the actual total number of tablets received over the expected total number of tablets to be received for a participant \times 100%.

Total time on study treatment for a specific period is calculated as the time in days from the first dose date until the last dose.

Total patient-years of exposure (years) for a specific period is calculated as the sum of total time on study treatment in a specific period across all participants who are treated.

In addition, the total number of participants with missed doses and reasons for missed doses will be summarized by treatment group and overall.

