# 6.1. Study Intervention(s) Administered

- ALXN2050 drug product will be provided as tablets that are manufactured using a common blend.
  - The 60 mg formulation will be used in Study ALXN2050-MG-201.
- Matching placebo will be manufactured in the same fashion, without the active ingredient. ALXN2050 and placebo tablets will be identical in appearance.
- The participant will be provided with sufficient study intervention to last until their next study visit. Additional details will be provided in the interactive response technology (IRT) manual.
- In order to maintain the study blind for participants, Investigators, and site personnel, each of the 2 daily doses will consist of 3 tablets that in combination correspond to the assigned treatment group.
  - 180 mg: three 60 mg tablets
  - 120 mg: two 60 mg tablets and one placebo tablet
  - Placebo: 3 placebo tablets
- During in-clinic visits, the participant will be administered the first dose of study intervention. The second dose of study intervention is to be taken at home. Whether in the clinic or at home, the timing of administration should be consistent.
- In the event of a missed dose, the participant should be instructed to take the study intervention within 6 hours of the originally scheduled time. If more than 6 hours have passed, the missed dose should be skipped. In either scenario, the next dose should be taken according to the original dosing schedule.

The specific details of study intervention are presented in Table 8.

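### SAP 5.6.1.1 builds planned and received dose in mismatched units, so relative dose intensity reads 300% at full adherence; the age formula in SAP 6.1.1 exceeds the SAP's own definition by 1 year

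*SAP*

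**What the plan says.** **Dose.** SAP 5.6.1.1 gives two amounts. The first begins "Planned total dose amount = assigned dose level of each tablet" and is completed by the daily frequency (bid) and the number of days. The second begins "Received total dose amount = assigned dose level of each tablet" and is completed by the number of tablets received, meaning dispensed minus returned. Relative dose intensity is then actual exposure over protocol-planned exposure, as a percentage; Protocol 9.4.5 says the same. For compliance, the same SAP section uses "Expected total number of tablets for a specific period = 6 tablets/day".

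Protocol 6.1 explains the six tablets: "each of the 2 daily doses will consist of 3 tablets that in combination correspond to the assigned treatment group". The 180 mg dose is three 60 mg tablets. The lower dose is "120 mg: two 60 mg tablets and one placebo tablet". Protocol Table 8 lists the dose level (120 or 180 mg bid) separately from the unit strength (60 mg).

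**Age.** SAP 6.1.1 first describes age as the number of years from the birth year to the reference year. It then gives a formula that takes that difference and adds 1. SAP 6.2.1 tabulates age at randomization below 65 against 65 or older.

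**Time units.** SAP 5.6.1.1 states: "Treatment duration will be calculated (in weeks) as the difference between the date of the last dose and the date of the first dose", plus 1. It also states: "Dose intensity is calculated as the total amount of the drug received divided by the treatment duration", and names no unit. Time on treatment is in days, yet "Total patient-years of exposure (years) for a specific period is calculated as the sum of total time on study treatment" across participants, with no divisor. SAP 5.6.1.2 likewise counts days when it defines patient-years for the adverse event rate.

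**The concern.** One term, dose per tablet, is multiplied by administrations in one formula and by tablets in the other. The two counts differ by a factor of three, so the ratio cannot be 100% for a fully adherent participant. It would contradict the compliance figure defined beside it, and a participant taking one third of the tablets would appear to be on full dose.

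The age rule contradicts itself within two sentences, and nothing in a finished table would reveal it. A mean age one year too high looks like any other mean age.

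The SAP addendum for the final report drops the exploratory, biomarker, sensitivity and supplementary analyses. It keeps the Section 5.6 safety analyses, the exposure summaries and the demographic tables. The affected outputs are therefore a sizeable part of what the abbreviated report will contain, and the addendum corrects none of these rules.

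**Working it through.** **Step 1. The SAP's own tablet count.** Protocol 6.1: 3 tablets x 2 doses = 6 tablets a day, which matches the compliance denominator in SAP 5.6.1.1. Over the 56-day Primary Evaluation Period that is 336 tablets.

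**Step 2. Relative dose intensity as written.** Let t be the dose per tablet and d the days. At full adherence:

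- planned = t x 2 x d
- received = t x 6 x d
- ratio = 6/2 = 300%, whatever t and d are (for placebo, t = 0 and the ratio is 0/0)

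With d = 56:

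| Arm | t (mg) | Planned (mg) | Received (mg) | Ratio | Protocol dose (mg) |
|---|---|---|---|---|---|
| 180 mg | 60 | 6,720 | 20,160 | 300% | 180 x 2 x 56 = 20,160 |
| 120 mg | 60 | 6,720 | 20,160 | 300% | 120 x 2 x 56 = 13,440 |
| 120 mg | 40 (mean over 3 tablets) | 4,480 | 13,440 | 300% | 13,440 |
| 120 mg | 120 | 13,440 | 40,320 | 300% | 13,440 |

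Which amount is wrong depends on what t means. At t = 40 the received amount is right and the planned amount is too small. At t = 120 the planned amount is right and the received amount is too large. The fault is the mismatch between the formulas, not one missing factor in one of them. As written, the ratio is 3 x adherence: 80% adherence reads 240%, and one-third adherence reads 100%.

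**Step 3. The charitable reading.** Take the regimen dose (180 or 120 mg) in the planned formula and 60 mg in the received one:

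- 180 mg arm: (60 x 6)/(180 x 2) = 100%
- 120 mg arm: (60 x 6)/(120 x 2) = 150%
- 120 mg arm, active tablets only: (60 x 4)/(120 x 2) = 100%

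This reading gives one phrase two meanings. It repairs the 120 mg arm only if placebo tablets are left out, and the received formula does not say so.

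**Step 4. Age.** Born 1960, reference year 2022: the definition gives 62 and the formula 63. Born 1958, reference year 2022: the definition gives 64 and the formula 65, which crosses the 65-year cut. The excess over the definition is always exactly 1.

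**Step 5. Time units.** The arm size is 70 x 2/5 = 28 participants. Over 56 days that is 28 x 56 = 1,568 days, or 1,568/365.25 = 4.29 patient-years. A duration of 56 days is 56/7 = 8 weeks. Neither division is written. The divisor 365.25 is my assumption.

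**Step 6. Check of the corrected formulas.** Planned = mg per administration x 2 x days. Received = (tablets taken/3) x mg per administration.

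- 180 mg arm: 336/3 x 180 = 20,160 mg against 20,160 mg planned, 100%
- 120 mg arm: 336/3 x 120 = 13,440 mg against 13,440 mg planned, 100%

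Partial adherence in the 120 mg arm, with 34 of 336 tablets returned (compliance 302/336 = 89.9%): the formula gives 302/3 x 120 = 12,080 mg. Of the 336 tablets, 224 are active. The true amount therefore lies between (224 - 34) x 60 = 11,400 mg, if every returned tablet is active, and 224 x 60 = 13,440 mg, if every one is placebo. The formula is between 6.0% too high and 10.1% too low.

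**The case against.** **The ratio is inferred.** The SAP does not say in so many words that relative dose intensity is the received total over the planned total. It speaks of actual and protocol-planned exposure, and protocol-planned exposure is unambiguous. This is fair. However, the two amounts are defined just above in the same section, and no other definition of exposure in mg is offered.

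**Dose level means the regimen elsewhere.** SAP 5.6.2.3, SAP 5.9 and Protocol Table 8 use the term for 120 or 180 mg bid, so the planned formula may be right and the received one wrong. That is possible. It changes which formula to edit but not the mismatch.

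**The units are labelled.** This largely stands. A reader might infer that adverse event rates will come out 365 times too low. The SAP labels the results in weeks, in years and per 100 patient-years, which tells a programmer to convert. The missing divisors are a drafting omission. Nor is a dose intensity of 20,160/56 = 360 mg per day wrong for 180 mg bid; the SAP simply does not state the unit.

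**The age formula is permissive and its effect unknown.** The SAP says ages may be computed this way, and no age distribution is given, so the number of participants moved cannot be stated. A reader might add that people aged 63 also cross the cut. That is so only for completed age, which is not the SAP's definition; on that definition only those aged 64 move.

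**Other documents may settle it.** The separate data presentation plan and the Week 8 addendum of 20 Dec 2023 were not available. Either may already correct some of this.

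**Conclusion.** The point holds as a specification error in descriptive outputs. Under the stated rules, and on the natural assumption that relative dose intensity is received over planned amount, it reads 300% at full adherence in both active arms. The only reading that rescues the 180 mg arm leaves 150% in the 120 mg arm unless placebo tablets are excluded. The age formula exceeds the SAP's own definition by exactly 1 year for everyone and moves those aged 64 into the older row. The unwritten divisors are minor.

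The documents do not show that any reported figure is wrong; they show only that the written rules would produce wrong figures if coded as they stand. No efficacy result, sample size or hypothesis test is touched. The correction is worth making because the addendum retains these tables and the change is small.

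**What to change.** - **Planned dose:** assigned mg per administration x 2 x days.
- **Received dose:** (tablets taken/3) x assigned mg per administration. Alternatively, use active tablets x 60 mg if returned tablets can be separated by kit after unblinding; the documents do not say whether they can. If they cannot, footnote that received mg is approximate in the 120 mg arm under partial adherence.
- **Relative dose intensity:** state that it is received over planned amount. For placebo, report tablet compliance only.
- **Age:** delete the + 1, use one definition throughout, and note that a calendar-year difference can exceed completed age by 1 year.
- **Units:** write /365.25 in SAP 5.6.1.1 and 5.6.1.2, write /7 for duration in weeks, and state the unit of dose intensity.

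The cost is a few lines of SAP or addendum text and the matching code, after a check of the data presentation plan and the Week 8 addendum. No new data are needed, and no efficacy analysis changes.

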5.6.1.2. Adverse Events

AEs will be coded in MedDRA Version 24.0 or higher. The National Cancer Institute Common Terminology Criteria for Adverse Events Version 5.0 will be used to grade the severity of the AEs. AEs during the Primary Treatment Period will be analyzed and reported in terms of TEAEs, which are defined as any AEs that started or worsened in severity on or after the first dose of study intervention and before the first dose in the ETP (if the participant discontinues during the PEP, TEAEs are any AEs that started or worsened in severity on or after the first dose of study intervention through 30 days after the last dose of study intervention). The same analysis will be performed, including the aggregated PEP, ETP, and OLE Period (if applicable) AE data up to the cutoff date during the ALXN2050 treatment period by dose received using the ALXN2050-Treated Set.

See Section 6.1.6 for judging the TEAEs for AEs with partial dates. In the case where it is not possible to define an AE as treatment emergent or not, the AE will be classified by the worst case (ie, treatment emergent).

The incidence of TEAEs will be summarized with frequency and percentage by MedDRA SOC and PT. In addition, the incidence of TEAEs will be summarized by severity and relationship to study intervention. Should a participant experience multiple events within a category, the participant will be counted only once for that category. Percentages will be based on the number of treated participants in the analysis set within a treatment group. For the ALXN2050 treatment period analysis, an event rate per 100 patient-years will also be presented, which is defined as the number of events occurred within 100 patient-years.

Event rate= number of events / patient-years × 100

Patient-years = sum of all patient-years for all participants in a treatment, where patient-years is defined as time in days from the first ALXN2050 dose to the earliest date (eg, the last ALXN2050 dose + 30 days, data cutoff date, or study discontinuation/completion date).

TEAE summaries will be produced by treatment arm.

The frequency tables will be ordered by SOC and PT in descending order of the frequency by total ALXN2050-treated participants. For SOCs or PTs with the same frequency, categories will be sorted alphabetically.

All AEs (prior and TEAE) will be listed.

AEs will include the displays described in the following subsections.

5.6.1.2.1. Overall Summary of AEs

An overall summary table of TEAEs will be presented using summary statistics (n, %). The number of events (m), number and percentage of participants with events, and the event rate of TEAEs per 100 patient-years will be displayed for the following events subcategories:

- Total number of TEAEs and participants with TEAEs
- Related TEAEs
- Not related TEAEs
- TEAEs toxicity by grades (Grades 1 to 5)
- TEAEs leading to study intervention discontinuation
- TEAEs leading to death
- TESAEs

- Related TESAEs
- Not related TESAEs
- TEAEs leading to study intervention discontinuation

5.6.1.2.2. TEAEs and TESAEs by SOC and PT

The number of TEAEs, the number and percentage of participants with events, and the event rate of TEAEs per 100 patient-years will be presented by SOC and PT. Participants are counted once in each SOC and PT. TESAEs will be summarized similarly.

5.6.1.2.3. TEAEs and TESAEs by SOC, PT, and Relationship

The number of TEAEs, the number and percentage of participants with events, and the event rate of TEAEs per 100 patient-years will be presented by SOC and PT as described above by relationship to study treatment (related and not related). If a participant has > 1 occurrence of an AE, the strongest relationship to study treatment will be used in the summary table. TESAEs will be summarized similarly.

5.6.1.2.4. TEAEs and TESAEs by SOC, PT, and Severity

The number of TEAEs, the number and percentage of participants with events, and the event rate of TEAEs per 100 patient-years will be presented by SOC and PT as described above by severity (Grades 1, 2, 3, 4, and 5). If a participant has > 1 occurrence of an AE, the highest grade will be used in the summary table.

5.6.1.2.5. Deaths and Other AEs

For TEAEs leading to study intervention discontinuation or death, the number of events, the number and percentage of participants with events, and the event rate of TEAEs per 100 patient-years will be presented by SOC and PT. Listings of TEAEs leading to study intervention discontinuation or death will be produced as well.

5.6.1.3. Additional Safety Assessments

All additional safety assessments will be reported by visit and treatment group.

5.6.1.3.1. Laboratory Tests

All laboratory data as of the data cutoff date will be included. Absolute values and changes from Baseline in central laboratory parameters (continuous variables) will be summarized descriptively at each visit by treatment group. Baseline is defined as the last nonmissing assessment value prior to the first dose of study intervention for the PEP. Shift tables over time will be presented for all laboratory values, where applicable, using normal, low, or high based on normal range values.

All central laboratory data will be presented in by-participant listings.

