- 10. Evidence of hepatitis B (hepatitis B positive hepatitis surface antigen [HbsAg] or positive hepatitis B core antibody [anti-HBc]) with negative surface antibody [anti-HBs] or hepatitis C viral infection (hepatitis C virus [HCV] antibody positive, except for patients with documented successful treatment and documented sustained virologic response [SVR]) at Screening.
- 11. History of malignancy within 5 years of the Screening Visit, with the exception of nonmelanoma skin cancer or carcinoma in situ of the cervix that has been treated with no evidence of recurrence.
- 12. History of persistent or recurrent infections prior to the Screening Visit.
- 13. Active systemic bacterial, viral, or fungal infection within 14 days prior to study intervention administration on Day 1.
- 14. Presence of fever as documented by a temperature  $\geq 38^{\circ}$ C (100.4°F) within 7 days prior to administration of study intervention on Day 1.
- 15. History or presence of any risk factors for Torsades de Pointes (eg, heart failure/cardiomyopathy or family history of Long QT Syndrome), a screening QT interval corrected using Fridericia's formula (QTcF) > 450 msec for males and > 470 msec for females, or receiving medications known to significantly increase the corrected QT interval (QTc).
- 16. Laboratory abnormalities at the Screening Visit, including:
  - a. Alanine aminotransferase  $> 2 \times$  the upper limit of normal (ULN)

- b. Direct bilirubin  $> 2 \times ULN$
- 17. Estimated glomerular filtration rate (eGFR) < 30 mL/min/1.73 m^2 and/or are on dialysis.
- 18. Any other clinically significant laboratory abnormality that, in the opinion of the Investigator, would make the participant inappropriate for the study or put the participant at undue risk.

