5. STATISTICAL ANALYSES

5.1. General Considerations

Summary statistics will be computed and displayed by visit, by treatment group, and overall, where applicable. The summary statistics for continuous variables will include, but will not be limited to, the number of participants, mean, SD, minimum, median, and maximum. For categorical variables, frequencies and percentages will be presented.

Inference from efficacy analyses will be based on a 2-sided type I error rate of 10% unless stated otherwise. No multiplicity adjustment will be implemented. Statistical analyses will be performed using the Statistical Analysis Software (SAS[®]) Version 9.4 or higher.

Medications will be coded using the World Health Organization Drug Dictionary (WHO DD; March 2021 or higher). Therapies will be coded using Medical Dictionary for Regulatory Activities (MedDRA; Version 24.0 or higher).

AEs will be coded by primary System Organ Class (SOC) and Preferred Term (PT) using MedDRA (Version 24.0 or higher).

5.1.1. Data Presentation for the First Analysis at Week 8

Data summaries for the analyses on the PEP data will be presented by 3 treatment groups ("Group 1: ALXN2050 180 mg bid", "Group 2: ALXN2050 120 mg bid" and "Group 3: Placebo"). Baseline is defined as the last measurement on or prior to the first dose of study intervention. For analysis including data beyond week 8, data summaries will be presented by 5 treatment groups ("Group 1: ALXN2050 180 mg bid", "Group 2: ALXN2050 120 mg bid", "Group 3: Placebo", "Group 3a: ALXN2050 180 mg bid" and "Group 3b: ALXN2050 120 mg bid"). Placebo group may be dropped for some of the analyses as specified in the respective sections. For all groups other than Groups 3a and 3b, baseline is defined as the last measurement on or prior to the first dose of study intervention. For Group 3a and 3b, two baselines will be defined for efficacy analysis: the PEP baseline is defined as the last measurement on or prior to the first dose of the PEP (primary baseline) and the ETP baseline is defined as the last measurement on or prior to the first dose of the Group 3a and 3b.

5.1.2. Data Presentation for the Second Analysis at Week 34

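### Laboratory shift tables use only low, normal and high, so large rises are not separated from small ones, and no planned table counts participants per arm by size of measured change

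*SAP*

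**What the plan says.** SAP 5.6.1.3.1 plans three laboratory outputs.

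- Descriptive statistics: "Absolute values and changes from Baseline in central laboratory parameters (continuous variables) will be summarized descriptively at each visit by treatment group". SAP 5.1 lists the statistics as "the number of participants, mean, SD, minimum, median, and maximum".
- Shift tables: "Shift tables over time will be presented for all laboratory values, where applicable, using normal, low, or high based on normal range values".
- Listings: "All central laboratory data will be presented in by-participant listings".

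The reference value is also set there: "Baseline is defined as the last nonmissing assessment value prior to the first dose of study intervention for the PEP". Protocol Table 2 schedules chemistry at both Screening and Day 1, so baseline will usually be the Day 1 value.

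Protocol 5.2, criterion 16, is introduced by "Laboratory abnormalities at the Screening Visit, including" and names ALT above 2 x ULN and direct bilirubin above 2 x ULN. Values above ULN and up to twice ULN at Screening are therefore eligible under that criterion.

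CTCAE enters the SAP only for adverse events (SAP 5.6.1.2): "Common Terminology Criteria for Adverse Events Version 5.0 will be used to grade the severity of the AEs". It is not applied to laboratory values. By contrast, SAP 5.6.1.3.2 counts participants who cross fixed vital-sign limits, and SAP 5.6.1.3.3 does the same for QT and QTcF. Each does so for the PEP in the Safety Set and for the ALXN2050 treatment period in the ALXN2050-Treated Set. The SAP addendum (section 1.2) keeps the section 5.6 safety analyses for the final report.

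**The concern.** Change from baseline in laboratory assessments is one of the two named safety endpoints, the other being TEAEs and TESAEs. The shift table is the only categorical laboratory analysis, and it records direction across the normal range, not size. Someone who enters above ULN has no higher category to move to. Someone who enters within range moves to the same cell whether the rise is slight or severe. A reader of the by-arm shift tables cannot tell these cases apart.

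The matter carries weight because the addendum drops the exploratory, biomarker, PK-parameter and exposure-response analyses but keeps safety in full. Safety is then a main part of what the final report delivers. In a trial of about 70 participants, a few marked changes in one arm could be the whole controlled signal.

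**Working it through.** The documents give no figure to reproduce on this point. The check applies the SAP's rule to example values.

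**Inputs**
- Shift categories: low, normal, high by normal range (SAP 5.6.1.3.1).
- Eligibility: ALT excluded only if above 2 x ULN at Screening (Protocol 5.2, criterion 16).
- Example values in multiples of ULN, chosen for illustration.
- Illustrative finer cut-points of >1, >2, >3, >5 and >8 x ULN. These are an assumption and do not come from the documents.

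**Rule.** A value is high if it exceeds 1 x ULN and normal otherwise; the low category plays no part for these values. The finer category is the number of cut-points exceeded.

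| Baseline | Post-baseline | Fold rise | SAP cell | Finer category |
|---|---|---|---|---|
| 0.8 | 1.2 | 1.2/0.8 = 1.50 | normal to high | 0 to 1 |
| 0.8 | 10 | 10/0.8 = 12.50 | normal to high | 0 to 5 |
| 1.01 | 10 | 10/1.01 = 9.90 | high to high | 1 to 5 |
| 1.5 | 3.1 | 3.1/1.5 = 2.07 | high to high | 1 to 3 |
| 1.5 | 10 | 10/1.5 = 6.67 | high to high | 1 to 5 |
| 2.0 | 10 | 10/2.0 = 5.00 | high to high | 1 to 5 |

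For the fifth row the absolute change is 10 - 1.5 = 8.5 x ULN, and the SAP table shows no shift. The first two rows share a cell although the rises differ greatly.

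**What the other summaries would show.** Randomizing 70 participants 2:1:2 gives 28, 14 and 28. With complete data, one participant rising by 8.5 x ULN moves the mean change of an arm of 28 by 8.5/28 = 0.30 x ULN, and of an arm of 14 by 8.5/14 = 0.61 x ULN. The maximum would show the value plainly, but it is one number per arm and visit: one participant or several at that level give the same maximum.

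**When samples are taken.** In the PEP, Protocol Table 2 schedules post-dose chemistry and hematology at Weeks 4 and 8 and at any Early Discontinuation or Clinical Deterioration visit. Protocol 8.2.4 adds repeats of clinically significant abnormal tests and allows unscheduled tests. SAP 6.1.5 bases by-visit summaries on nominal visits, so a peak found on an unscheduled repeat may appear only in a listing.

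**The case against.** The strongest reply is that the information is reported elsewhere. By-visit change from baseline includes the maximum, so a rise of 8.5 x ULN would stand out, and every central laboratory value is listed. Protocol 8.2.4 sends clinically relevant laboratory changes to the AE form, and Protocol 10.3.1 counts clinically significant abnormal results as AEs. SAP 5.6.1.2.4 then tabulates participants by preferred term and Grades 1 to 5. In about 70 participants, one or two severe cases would be found. The named endpoint is analysed and nothing contradicts the protocol. Table 5 of the protocol lists meningococcal infection, seizure, and pregnancy or lactation exposure as potential risks, not liver injury. The trial is exploratory, with no formal safety testing.

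Much of this stands. The values are not lost, the endpoint is covered, and a per-arm participant count by severity does exist for changes that the investigator judges clinically significant. Three limits remain.

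- That count depends on judgement, and the intensity scale in Protocol 10.3.3 is worded by symptoms and function, so a large rise without symptoms need not receive a high grade.
- Listings are not by-arm summaries, and maxima do not count participants.
- The SAP adds threshold counts for vital signs and QT/QTcF although those data also have by-visit summaries and listings.

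A reader might go further and infer that the plan cannot distinguish severe from trivial laboratory change at all, that Weeks 4 and 8 are the only placebo-controlled samples, or that a liver signal is suspected. The documents support none of these. The maxima, listings and graded TEAEs answer the first. The Early Discontinuation, Clinical Deterioration, repeat and unscheduled tests answer the second. On the third, the protocol's risk table names no hepatic risk.

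**Conclusion.** The point holds as a gap in tabulation. Given a baseline above ULN, every later value above ULN is recorded as high to high; given a normal baseline, mild and severe rises share one cell. This follows from the SAP's rule without further assumption. What is missing is a by-arm count of participants by size of the measured change.

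How often it matters cannot be sized. The documents do not give the number of participants starting above ULN. The 2 x ULN limit applies at Screening while baseline is the last pre-dose value, so a baseline may have returned to normal or may exceed 2 x ULN. Criterion 18 also lets the investigator exclude other clinically significant abnormalities. The same limitation applies to direct bilirubin and to any analyte already abnormal at baseline. This is a worthwhile, inexpensive improvement in reporting and not a threat to the trial's conclusions.

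**What to change.** Add worst post-baseline tables to SAP 5.6.1.3.1, including unscheduled values, by arm for the PEP (Safety Set) and for the ALXN2050 treatment period (ALXN2050-Treated Set):

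- number and percentage of participants by prespecified multiples of ULN for ALT, AST and total bilirubin, and for the enzymes and bilirubin in combination;
- baseline-to-worst shifts by CTCAE v5.0 grade for gradable parameters, using the version the SAP already applies to AEs.

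The cut-points are a reporting choice and do not come from the documents; >3, >5 and >8 x ULN for ALT and AST and >2 x ULN for bilirubin would serve as an example. If the SAP is closed, put the tables in the clinical study report and label them post hoc.

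Protocol Table 11 already collects these tests, so no new samples or visits are needed. The cost is programming and checking several tables in two periods and two analysis sets.
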